7.2.4 Weighting of Enrolled Patients

In the TITE-CRM algorithm, patients are weighted in the calculation of the dose-toxicity function according to the proportion of the DLT observation period they have completed. Patients who have experienced DLT are assigned full weight (1), patients who have completed the eight-week post-treatment observation period without DLT are assigned full weight and patients still within the eight week post-treatment period, who have not experienced DLT are assigned a weight proportional to the fraction of the observation period they have completed. Because treatment will be completed within two weeks, the total observation period for the purposes of TITE-CRM will be assumed to be ten weeks from the day of the first fraction.

7.2.5 Operating characteristics

The operating characteristics of the trial design were evaluated in a simulation experiment. 750 TITE-CRM trials were simulated assuming the toxicity probabilities in Table 7.1, but with true toxicity probabilities as specified in Table 7.2. In simulations of Scenerio1, the assumed probabilities of toxicity are correct, but in Scenerio 2, the true probability is higher than assumed, and in Scenerio3 there is a jump in toxicity over the target rate between 27 Gy and 30 Gy.

Radiation Dose	Expected Probability of DLT	True Probabilities of DLT		
		Scenario 1	Scenario 2	Scenario 3
24 Gy	0.08	0.08	0.10	0.10
27 Gy	0.11	0.11	0.15	0.15
30 Gy	0.14	0.14	0.20	0.35
33 Gy	0.17	0.17	0.25	0.55
36 Gy	0.20	0.20	0.30	0.75

Table 7.2. Conditions for Monte Carlo Assessment of Operating Characteristics

The operating characteristics are described in Figure 7.1. Metrics described are numbers of patients treated at each dose, number of observed toxicity per dose, selected MTD and number of observed toxicity per trial. Roughly equal numbers of patients are treated at each dose in the first scenario (where the trial assumptions match the true probabilities of toxicity), with decreasing numbers of patients treated at higher doses in the second and third scenarios. In the second and third scenarios, medians of 0 or 1 DLT per trial result from treatment at doses of 33 or 36 Gy. The chosen target dose tends to be somewhat conservative in all three scenarios. In the third scenario, in 56% of the trials result in either 24% or 28% of the patients on study experiencing DLT, due to the large jump

in toxicity across the true target dose, while, in the other scenarios, the proportions of patients on study experiencing DLT is less than or equal to the target rate of 1/6 in over 70% of the simulated trials. The proportions of treated patients experiencing DLT are similar to what would be expected from the 3+3 design, while the accuracy of the TITE-CRM design is actually slightly conservative compared to 3+3.

[figure not shown]

Figure 7.1 Operating characteristics of trial design. Bars from left to right in all frames indicate the first, second and third scenarios (Table 7.2). In the top frames, the tick marks indicate the medians, and the top and bottom of the bars the 97.5th and 2.5th percentiles, respectively. Asterisks in the bottom left frame indicate the true target doses for the three scenarios

7.4 Sample Size/Accrual Rate

No more than 25 evaluable patients will be treated in the trial. An evaluable patient is defined as one who either a) completes the three fractions and has no DLT until one month after the last fraction, or b) a patient who received at least one fraction and suffers DLT. Patients who are not evaluable will be replaced.

7.3 Data Analysis

When possible, generalized linear models (subsuming, for example, logistic regression) will be used to combine data from different dose levels. Model assumptions will be checked graphically prior to analysis. If model assumptions are not met, the analysis will be primarily descriptive. Baseline description statistics on all evaluable patients will be provided for demographic variables (age, sex, race/ethnicity), Karnofsky performance status, disease stage and status at the time of enrollment and treatment regimens previously used.

7.3.1 Analysis of the Primary Endpoint

1. Toxicities will be tabulated by category and grade. The proportion patients experiencing DLT at each dose will be calculated with 95% exact confidence intervals. The dose-toxicity function, describing the probability of DLT at each dose, will be estimated using logistic regression, along with likelihood ratio profile confidence intervals.

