7.0 Statistical Considerations

7.1 Definitions

Primary Objective

To determine the maximum tolerated dose (MTD) and safety of fractionated SRS when treating brain metastases

- Primary Endpoint: Maximum Tolerated Dose: the maximum amount of Gy fractionated stereotactic radiosurgery (FSRS) delivered without significant toxicity

Secondary Objectives

To evaluate the local control associated with this therapy.

To evaluate regional intracranial failure associated with this therapy.

To evaluate the Health Related Quality of Life (HRQL) associated with this therapy.

Secondary Endpoints

- Local control: proportion of patients with Complete Response (CR), Partial Response (PR), or Stable Disease (SD) in the target lesion
- Regional intracranial failure: proportion of patients that develop new lesions outside the target volume
- Health Related Quality of Life (HRQL) measured by Functional Assessment of Cancer Therapy – General (FACT-Brain) assessment.

The following definitions will be useful in explaining the trial design.

7.1.1 *Toxicity*

In this section, *toxicity* is taken to mean unacceptable, dose-limiting toxicity, as defined in Section 5.2.4, as any adverse event that occurs between the first fraction of radiotherapy and 60 days after the last fraction of radiotherapy. The primary goal of the TITE-CRM design employed in this trial is to identify the radiation dose associated with toxicity in 1/6=16.7% of patients (the MTD); this is referred to as the *target rate*.

7.1.3 *Expected rates of toxicity*

Based on previous treatment experience, the *expected rates of toxicity* have been estimated (Table 7.1). These rates will be re-evaluated throughout the trial as treatment experience is accrued in accordance with the TITE-CRM algorithm.

Radiation Dose	Expected Probability of Acute Toxicity
24 Gy	0.08
27 Gy	0.11
30 Gy	0.14
33 Gy	0.17
36 Gy	0.20

Table 7.1. Expected probabilities of toxicity

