7.2.3 Dose-Toxicity Function

Given total dose d , a logistic dose-toxicity model with parameter α ,

$$P(DLT|d) = e^{3+\alpha d} / (1 + e^{3+\alpha d}),$$

Will be used, where $\alpha=1.0$ represents the initial assumptions about the toxicity of treatment, as displayed in the 'Design' column of Table 7.1. This model, which has been widely used in CRM trials (24,26-29), is an approximation to the true, unknown, dose-toxicity model. The first two patients will be assigned to Level 1. When subsequent patients present for

enrollment, the expected probability of toxicity at each dose will be calculated, based on the prior distribution of α (Gaussian, with mean of 1 and standard deviation of 0.3) and the available data, using a SAS computer routine written especially for this application. The patient will be assigned to the level with estimated probability of toxicity closest to but not exceeding the target rate, 0.167, allowing for the escalation restrictions in Section 7.2.2.

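### Section 7.3.1 leaves the final TITE-CRM estimate out of the primary output; adding it at the selected dose would report DLT risk more precisely in Scenarios 1 and 2, at almost no cost

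*Combined protocol and SAP*

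**What the plan says.** Section 7.1.1 gives the TITE-CRM its task: to "identify the radiation dose associated with toxicity in 1/6=16.7% of patients (the MTD"). Section 7.2.3 supplies a one-parameter logistic model with the intercept fixed at 3 and a Normal(1, 0.3) prior on alpha. It also gives the allocation rule: "The patient will be assigned to the level with estimated probability of toxicity closest to but not exceeding the target rate, 0.167". In that model alpha = 1 "represents the initial assumptions about the toxicity of treatment", that is, the rates in Table 7.1.

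Section 7.3.1, on the primary endpoint, lists toxicity tables, the DLT proportion at each dose with exact 95% intervals, and a regression: "The dose-toxicity function, describing the probability of DLT at each dose, will be estimated using logistic regression, along with likelihood ratio profile confidence intervals". It does not mention the final posterior, the model-based DLT probabilities or the selected MTD. Section 7.3 adds a general fallback: "If model assumptions are not met, the analysis will be primarily descriptive". Section 7.4 caps the trial at 25 evaluable patients. Sections 3.3 and 5.2.3 already declare an MTD but do not show the estimate behind it.

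**The concern.** The model that carries the dose decision is missing from the output that reports it. Section 1 of the plan's rationale says the trial is to supply a safe dose for Phase II and III trials, and a reader planning such a trial would want the DLT risk on which the choice rests. Section 7.3.1 would show two other estimates instead. The exact intervals use only the patients at one dose and are wide. The regression, if it has a free intercept and a free slope, must estimate both from a handful of DLTs in at most 25 patients, and with so few events the fit may not exist. The more stable estimate is already computed by the SAS routine that Section 7.2.3 describes.

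**Working it through.** **Inputs from the documents.** DLT rates 0.08, 0.11, 0.14, 0.17, 0.20 (Table 7.1); target 1/6; the model and prior of Section 7.2.3; the escalation limits of Section 7.2.2; ten-week weights (Section 7.2.4); 25 patients; Scenarios 1–3 (Table 7.2).

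**Step 1: reproduce Table 7.1.** The model is logit P = 3 + alpha × d. With total Gy and alpha = 1, the lowest level gives 3 + 24 = 27, so P > 0.999999 there and at every higher level. To return Table 7.1, d must be the label logit(p) − 3. For example, logit(0.20) = −1.386, so the label is −4.39. The five labels are −5.44, −5.09, −4.82, −4.59 and −4.39. They are used below.

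**Step 2: compare with the figures in Section 7.2.5.** With a simulated TITE-CRM under the protocol rule, the statement that over 70% of trials keep the DLT share at or below 1/6 is met in Scenario 1 (73–94%). In Scenario 2, using the plug-in estimate, it is met only with fast accrual (82% and 72% at one patient every one or two weeks; 52–60% at four weeks or slower). The 56% quoted for Scenario 3 was not reached (8–31%). Accrual rate, DLT timing, the routine's estimator and Figure 7.1 are unavailable, so this does not show an error in the plan. It does mean the match to the plan's own simulation is unverified.

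**Step 3: one worked example (assumed data).** Patients 4/3/3/5/10 at the five levels, one DLT each at 33 and 36 Gy. The CRM posterior is proportional to exp[−(alpha − 1)²/(2 × 0.3²)] × Π P^y (1 − P)^(n − y). P(DLT) at 36 Gy:

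| Method | Estimate | 95% interval |
|---|---|---|
| Exact | 10.0% | 0.3–44.5% |
| Intercept plus slope, profile likelihood | 13.9% | 1.9–41.1% |
| One-parameter likelihood | 10.5% | 2.0–27.5% |
| CRM, posterior mean | 12.3% | 3.2–26.7% |

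The CRM plug-in estimate is 10.9%, so the summary used has to be named. With both DLTs at 36 Gy, the two-parameter fit goes to its boundary, 20.0% (3.6–49.9%), and the CRM gives 12.1% (3.1–26.5%).

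**Step 4: expected information.** Take 5 patients per dose at the Table 7.1 rates. The standard error of logit P at 36 Gy is 0.91 for two parameters, 0.53 for one parameter without the prior, and 0.49 for the CRM. Around 20%, −1.386 ± 1.96 × SE gives 4.0–59.8% for two parameters and 8.7–39.7% for the CRM.

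**Step 5: simulation at the selected dose.** There were 1,000 trials in each of 12 settings per scenario. Assumptions not in the documents: random accrual at 0.5, 1 or 2 per month; DLT times uniform or late over ten weeks; posterior-mean or plug-in estimate; complete final follow-up; selection among levels already used. The planned output is represented by the two-parameter fit where the slope is finite and the exact proportion otherwise. Ranges run over the 12 settings; errors and widths are in percentage points.

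| | Scenario 1 | Scenario 2 | Scenario 3 |
|---|---|---|---|
| Root-mean-square error, planned output | 9.8–13.6 | 10.4–13.4 | 9.6–13.1 |
| Root-mean-square error, CRM | 5.8–6.5 | 7.6–8.7 | 8.6–12.0 |
| Root-mean-square error, one-parameter regression | 7.0–7.6 | 8.2–9.0 | 9.3–12.4 |
| Median interval width, planned output | 33–45 | 31–36 | 29–32 |
| Median interval width, CRM | 25–26 | 26–27 | 26–27 |
| Coverage, planned output | 97–99% | 96–98% | 94–97% |
| Coverage, CRM | 93–97% | 91–96% | 80–87% |
| No finite two-parameter slope | 17–31% | 12–21% | 11–22% |

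The error ratio in Scenarios 1 and 2 runs from 10.4/8.7 = 1.2 to 13.6/5.8 = 2.3. Repeat simulations agree closely: no finite fit in 12–31% and 15–30% of trials, and CRM error lower at the selected dose in all three scenarios.

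**Step 6: away from the selected dose.** In Scenario 3 the CRM's 95% interval covered the truth in about 55–85% of trials at 30 Gy, 1–2% at 33 Gy and 0% at 36 Gy.

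**The case against.** The strongest reply is that the CRM buys its precision with a fixed intercept and a prior. Scenario 1 is that prior, and Scenario 2 is a smooth shift from it. Where the shape is wrong, as when "in Scenerio3 there is a jump in toxicity over the target rate between 27 Gy and 30 Gy", the gain nearly vanishes and coverage suffers. In the example, moving a DLT from 33 to 36 Gy lowers the CRM estimate at 36 Gy from 12.3% to 12.1%, although the raw rate there doubles from 1/10 to 2/10: the model hardly registers where DLTs occur. The planned intervals keep 94–99% coverage in all three scenarios. Using the CRM to allocate and prior-free intervals to report is a defensible choice. All of this stands. It rules out a stronger reading that a reader might infer, that the CRM posterior should become the primary estimate at every level with the regression demoted. Step 6 shows why.

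It is also true that Section 7.3.1 does not state the number of parameters, and that Section 7.2.3 uses the same term for its one-parameter model. On that reading little is lost. Two things favour the two-parameter reading: Section 7.3 speaks of generalized linear models at large, and Section 7.3.2 uses the same sentence for local control, which has no CRM. The comparator in Step 5 is a construct too, since the plan would report both the regression and the exact intervals and does not define when the fallback applies.

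A reader might also see a conflict in weighting. In the CRM, a DLT-free patient still under observation is "assigned a weight proportional to the fraction of the observation period they have completed", whereas Section 7.4 counts as evaluable one who "completes the three fractions and has no DLT until one month after the last fraction". Once ten weeks of follow-up are complete every weight is 1, so this is not part of the point.

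**Conclusion.** The point holds as a gap in reporting. Section 7.3.1 omits the final estimate from the only rule described for finding the MTD. On the two-parameter reading, the planned output carries about 1.2–2.3 times the CRM's error at the selected dose in Scenarios 1 and 2, and the regression has no finite solution in roughly 12–31% of trials. In Scenario 3 the gain is small, and on the one-parameter reading the difference is small throughout. These sizes rest on the assumed accrual, DLT timing and fallback trigger, and on the routine having used the Step 1 labels.

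A reader might infer that the plan has two competing rules for the MTD, or that the declared MTD is wrong. The documents support neither. No sentence says how the MTD is read off after the last patient, but Sections 7.1.1 and 7.2.2–7.2.3 describe no rule other than the TITE-CRM. Nothing here bears on which dose is right.

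**What to change.** Add to Section 7.3.1 the final TITE-CRM estimate of P(DLT) at the selected dose with a 95% credible interval, beside the exact intervals and the logistic regression and not in place of them. In the same edit:

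- Name the posterior summary, and use the one that was used for allocation.
- Correct Section 7.2.3 so that d is a dose label (−5.44, −5.09, −4.82, −4.59, −4.39) and not total Gy, after confirming the labels in the SAS routine.
- State whether the logistic regression has one parameter or two.
- State the limits: the CRM interval depends on the fixed intercept and prior; it hardly responds to which dose the DLTs occurred at; it covers only about 80–88% at the selected dose in Scenario 3 (the repeat run extends the tabled range slightly); and it should not be relied on above the selected dose, where coverage in that scenario falls to about 0–2% at 33 and 36 Gy.
- Because the MTD is already declared, label the addition as made after the data were known.

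The cost is SAP wording and a few lines from an existing routine, with no extra patients, visits or data. The drawback is that a narrower, model-dependent interval may be over-read, which is why the exact intervals must stay beside it.

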7.3.2 Analysis of Secondary Endpoints

2. The proportion patients experiencing local control at each dose will be calculated with 95% exact confidence intervals. The dose-response function, describing the probability of local control at each dose, will be estimated using logistic regression, along with likelihood ratio profile confidence intervals.
3. The probability of failure will be analyzed in a similar fashion to the probability of intracranial failure.
4. The analysis of HRQL data (Section 6.5.1.4) will be descriptive. The data will be summarized by question at each time point with the frequency and percentage of each quality level. For each patient, the trajectory of the score will be plotted against time.

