6.4 Objective criteria for defining response

6.4.1. Tumor Response on MRI (RECIST)

Measurable Disease Response: CTEP's RECIST guidelines will be followed. A quick reference to the RECIST guidelines can be downloaded at the following URL:

<http://ctep.info.nih.gov/Policies/WordDocs/RCSTF.PH2TEMPF.doc>. (Appendix II)

Patients enrolled in this study must have a measurable brain metastasis which is defined as lesions that can be accurately measured in at least one dimension: [longest diameter to be recorded] on the MRI scan.

The same method of assessment and the same technique should be used to characterize each identified & reported lesion at baseline & during follow-up.

Taking into account the measurement of the longest diameter only for those lesions with size response, response criteria are defined as:

1. Complete Response (CR): the disappearance of a target lesion. Any pathological lymph nodes (whether target or non-target) must have reduction in short axis to <10 mm.
2. Partial Response (PR): at least a 30% decrease in the sum of diameters of target lesions, taking as reference the baseline sum diameters.
3. Progressive Disease (PD): at least a 20% increase in the sum of diameters of target lesions, taking as a reference the smallest sum on study (this includes the baseline sum if that is the smallest on study). In addition to the relative increase of 20%, the sum must also demonstrate an absolute increase of at least 5 mm. (Note: the appearance of one or more new lesions is also considered progression).
4. Stable Disease (SD): neither sufficient shrinkage to qualify for partial response nor sufficient increase to qualify for progressive disease, taking as reference the smallest sum diameters while on study.²¹

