6.4.1.2 Definition of local control

In this study, patients will be recorded as having a lesion that is locally controlled if they have stable disease (SD), partial response (PR), or complete response (CR) in the target lesion; all of which are defined above. Patients will be recorded as having local failure if they have progressive disease (PD) within the target lesion. Patients that develop new lesions outside the target volume will be coded as having a regional intracranial failure. A distant failure will be defined as new brain metastases outside of the treatment volume.

6.4.1.3

HRQL studies (Fact-Brain) will be completed prior to treatment, and following treatment to coincide with follow-up exams and MRI scans. See appendix III for a full version of the Fact-Brain questionnaire.

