- The main goal of confirmation of objective response is to avoid overestimating the response rate observed. In cases where confirmation of response is not feasible, it should be made clear when reporting the outcome of such studies that the responses are not confirmed.
- To be assigned a status of PR or CR, changes in tumor measurements must be confirmed by repeat assessments that should be performed no less than 4 weeks after the criteria for response are first met. Longer intervals as determined by the study protocol may also be appropriate.
- In the case of SD, follow-up measurements must have met the SD criteria at least once after study entry at a minimum interval (in general, not less than 6-8 weeks) that is defined in the study protocol

Duration of overall response

- The duration of overall response is measured from the time measurement criteria are met for CR or PR (whichever status is recorded first) until the first date that recurrence or PD is objectively documented, taking as reference for PD the smallest measurements recorded since the treatment started.

Duration of stable disease

- SD is measured from the start of the treatment until the criteria for disease progression are met, taking as reference the smallest measurements recorded since the treatment started.
- The clinical relevance of the duration of SD varies for different tumor types and grades. Therefore, it is highly recommended that the protocol specify the minimal time interval required between two measurements for determination of SD. This time interval should take into account the expected clinical benefit that such a status may bring to the population under study.

Response review

- For trials where the response rate is the primary endpoint it is strongly recommended that all responses be reviewed by an expert(s) independent of the study at the study's completion. Simultaneous review of the patients' files and radiological images is the best approach.

Reporting of results

- All patients included in the study must be assessed for response to treatment, even if there are major protocol treatment deviations or if they are ineligible. Each patient will be assigned one of the following categories: 1) complete response, 2) partial response, 3) stable disease, 4) progressive disease, 5) early death from malignant disease, 6) early death from toxicity, 7) early death because of other cause, or 9) unknown (not assessable, insufficient data).

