- All of the patients who met the eligibility criteria should be included in the main analysis of the response rate. Patients in response categories 4-9 should be considered as failing to respond to treatment (disease progression). Thus, an incorrect treatment schedule or drug administration does not result in exclusion from the analysis of the response rate. Precise definitions for categories 4-9 will be protocol specific.
- All conclusions should be based on all eligible patients.
- Subanalyses may then be performed on the basis of a subset of patients, excluding those for whom major protocol deviations have been identified (e.g., early death due to other reasons, early discontinuation of treatment, major protocol violations, etc.). However, these subanalyses may not serve as the basis for drawing conclusions concerning treatment efficacy, and the reasons for excluding patients from the analysis should be clearly reported.
- The 95% confidence intervals should be provided.

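### Local control is analysed as a crude proportion with no assessment time, so the figure depends on survival and length of follow-up

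*Combined protocol and SAP*

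**What the plan says.** Section 7.1 defines the endpoint: "Local control: proportion of patients with Complete Response (CR), Partial Response (PR), or Stable Disease (SD) in the target lesion". Section 7.3.2 gives the analysis: "The proportion patients experiencing local control at each dose will be calculated with 95% exact confidence intervals", followed by a logistic regression of local control on dose. Section 6.4.1.2 gives the failure rule: "Patients will be recorded as having local failure if they have progressive disease (PD) within the target lesion". It says nothing about death or a missing scan.

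Sections 6.2 and 6.2.1 provide for follow-up to 24 months or death, with the first MRI at 8-12 weeks after treatment and further scans every 8-12 weeks.

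On response, section 6.4.1 says that "RECIST guidelines will be followed". The generic RECIST reference in Appendix I adds "All patients included in the study must be assessed for response to treatment, even if there are major protocol treatment deviations", lists early death and unknown status among its outcome categories, and says of the response rate: "Patients in response categories 4-9 should be considered as failing to respond to treatment (disease progression". It leaves the exact definitions of those categories to the protocol, which supplies none.

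Under section 7.4 a patient is evaluable who "completes the three fractions and has no DLT until one month after the last fraction", or who receives at least one fraction and has a DLT. "Patients who are not evaluable will be replaced". The section does not say that this set is the denominator for local control.

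**The concern.** A patient who survives two years is scanned roughly 8 to 13 times (104/12 to 104/8). A patient who dies at four months is scanned once or twice. Both enter the same proportion, and the plan does not say at which time, or on which scan, status is read. Short survival or early removal leaves less opportunity to record progression, so the PD-only proportion rises when patients die sooner, even if the tumors behave identically.

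The background section reports the site's earlier series as actuarial local control of 80% at 6 months and 74% at 12 months. A crude proportion over unspecified follow-up estimates something else. The earlier figures are background and not a formal benchmark, but they are the natural comparison.

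A second, smaller gap concerns patients with no post-treatment MRI. A patient can become evaluable one month after the last fraction, before the first scan is due. How such a patient counts is not stated, and the choice could be made after the data are seen.

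**Working it through.** The plan states no target rate, power or sample size for local control, so there is no figure of its own to reproduce. The calculation below shows how far the crude proportion can move for one fixed tumor process.

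**Inputs from the protocol.** Actuarial control of 80% at 6 months and 74% at 12 months, and a 30-week median survival after two-fraction treatment in a cited series (background section); first MRI at 8-12 weeks (6.2.1); evaluability at one month after the last fraction (7.4); at most 25 evaluable patients over five dose levels (7.4, 5.2.3).

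**Assumptions.** The documents give no expected survival for this trial. The 30-week figure comes from a series of tumors under 3 cm whose cited title refers to recurrent metastases, so longer survival is shown as well. Death occurs at 5 weeks plus an exponential time with median m = 30, 52 or 104 weeks, so the actual medians are 35, 57 and 109 weeks. Death is independent of local failure. Progression is dated when it occurs. The hazard for months 6-12 is carried forward to 24 months.

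**Local-failure hazards.** 0-6 months: -ln(0.80)/0.5 = 0.446 per year. After 6 months: -ln(0.74/0.80)/0.5 = 0.156 per year.

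**PD-only proportion at time t.** One minus the integral from 0 to t of (local-failure density) x (probability of being alive). For the 35-week median, the death hazard after week 5 is ln 2/(30/52) = 1.201 per year. At 12 months the integral has three parts:

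- weeks 0-5: 0.042
- week 5 to month 6: 0.126
- months 6-12: 0.028

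The sum is 0.196, so the proportion is 1 - 0.196 = 0.804.

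| Median survival | 6 months | 12 months | 24 months |
|---|---|---|---|
| 35 weeks | 83% | 80% | 78% |
| 57 weeks | 82% | 78% | 74% |
| 109 weeks | 81% | 76% | 70% |
| Actuarial (same tumors) | 80% | 74% | 63% (extrapolated) |

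With a true 30-week median (5 weeks plus an exponential with median 25), the 12-month figure is 81%.

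**Patients with no post-treatment MRI.** For the 35-week median, the share dying before a first scan at week w is 1 - exp(-1.201 x (w - 5)/52). This is 6.7% for week 8 and about 15% for week 12. At 12 months:

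| Median survival | Counted as failures | Excluded |
|---|---|---|
| 35 weeks | 67-74% | 78-79% |
| 57 weeks | 70-74% | 77% |
| 109 weeks | 72-74% | 75-76% |

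If nobody dies before the first scan, the coding question disappears.

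**Sampling error.** 20 of 25 controlled (80%) has an exact 95% interval of 59-93%, a half-width of about 17 points. With an average of 25/5 = 5 patients per dose, 4 of 5 has an exact interval of 28-99%.

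**What a time-to-event analysis would deliver.** Simulated trials of 25 patients, with scans every 10 weeks and the 35-week median, give about 4.4 local failures by 12 months and about 3 patients with no post-treatment MRI. The 12-month Kaplan-Meier estimate averages 74%, with a central 95% range of about 49-95%. With the 57-week median there are about 5.1 failures and the range is 53-92%.

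**The case against.** The strongest reply is that this is a secondary endpoint in a phase I trial of 25 patients. The MTD does not depend on it, definitive efficacy is left to later trials, and every shift above is smaller than the sampling error. That stands, and it limits the weight of the point. It does not remove it: the exact interval is computed after the coding choice and does not reflect a systematic shift.

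A second reply is that a proportion is legitimate, and that cumulative incidence with death as a competing event depends on survival too. This also stands. With full follow-up, the PD-only proportion at a stated time equals one minus that cumulative incidence. The defect is the unnamed time, follow-up and coding, not the use of a proportion as such.

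A reader might infer that section 6.4.1.2 and Appendix I count death and missing MRI in contradictory ways. The documents do not support that. Section 6.4.1.2 is silent on both. The Appendix I rule is generic, concerns the response rate and early death, and leaves definitions to the protocol. A patient with documented stable disease who later dies is not clearly coded differently by the two texts. The ambiguity is confined to patients with no post-treatment MRI.

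**Conclusion.** The point holds as a cheap improvement to a secondary analysis. For tumors with 74% actuarial control at 12 months, the PD-only proportion would read about 2 to 6 points higher (76-80%) under the survival assumptions shown. For the 35-week median it would read 83%, 80% or 78% depending on whether it is taken at 6, 12 or 24 months. Coding of unscanned patients adds a difference of roughly 4 to 12 points in that case (67-74% against 78-79%), and nothing if no one dies before the first scan.

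The sizes rest on assumed exponential, independent survival after week 5 and on a hazard fitted to the site's earlier series. The direction does not depend on the exact values. A reader might also infer a spurious dose trend or a threat to the primary endpoint. Neither follows: with full follow-up and equal survival across doses no trend is expected, and the MTD rests on DLTs.

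**What to change.** In section 7.3.2, define local failure as time from the first fraction to PD of the lesion treated with fractionated radiosurgery. Report, overall and descriptively by dose:

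- Kaplan-Meier estimates at 6 and 12 months, with patients without local PD censored at their last MRI, for comparison with actuarial series;
- cumulative incidence of local failure with death as a competing event, since many patients may die without local failure.

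A proportion at a named time with a named coding rule may be kept alongside. Name the denominator, report how many patients have no post-treatment MRI, and state the data cut-off. State that section 6.4.1.2, and not the Appendix I rule for categories 4-9, governs local control. Label any dose model exploratory, given about 4 to 5 expected events by 12 months. Rewrite item 3 of section 7.3.2, which refers to an intracranial-failure analysis that is not described, so that regional intracranial failure is analysed in the same way.

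The cost is wording and standard code, because the scans are already scheduled. The downsides are a little more analysis work and wide intervals (about 49-95% for the 12-month Kaplan-Meier estimate in repeated trials). The 6-month estimate is also sensitive to scan timing: with scans every 10 weeks it averages 84% against a true 80%, because the last scan before 6 months falls at week 20. Sections 3.3 and 5.2.3 say that the MTD has been determined, so the change should be dated and disclosed as made after treatment began.
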